8.9. Sample Size

Sample size is determined based on the superiority test of filgotinib 200 mg in combination with MTX compared to MTX alone based on the change from Baseline in mTSS at Week 24. When assuming a difference of 0.62 between the two groups and a common standard deviation of 2.7, 400 subjects in the filgotinib 200 mg in combination with MTX group and 400 in the MTX alone group are required to obtain 90% power at a 2-sided 0.05-level.

The total sample size will be 1200 (400 subjects for filgotinib 200 mg in combination with MTX group, 200 subjects for filgotinib 100 mg in combination with MTX, 200 subjects for filgotinib 200 mg alone group and 400 subjects for MTX alone group). This sample size will provide over 90% power to detect an increase in ACR20 response rate of 62% to 78% between the MTX alone group and each of the filgotinib groups respectively, using a 2-sided 0.05-level test.

8.10. Data Monitoring Committee

An external multidisciplinary DMC will review the progress of the study and perform interim reviews of safety data and provide recommendation to Gilead whether the nature, frequency, and severity of adverse effects associated with study treatment warrant the early termination of the study in the best interests of the participants, whether the study should continue as planned, or the study should continue with modifications.

The initial reviews will be conducted after approximately 100 subjects enrolled complete 12 weeks treatment. The DMC's specific activities will be defined by a mutually agreed charter, which will define the DMC's membership, conduct and meeting schedule.

While the DMC will be asked to advise Gilead regarding future conduct of the study, including possible early study termination, Gilead retains final decision-making authority on all aspects of the study.

8.11. Cardiovascular Endpoint Adjudication Committee

A Cardiovascular Endpoint Adjudication Committee (CV-SEAC) consisting of at least 2 cardiologists and governed by a Charter will be set up to perform adjudication of Major Adverse Cardiovascular Events occurring during the study. The adjudication of these events will be performed in a blinded fashion for the purposes of data analysis, and not for monitoring of subject safety.

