## **7. SAFETY ANALYSES**

### **7.1. Adverse Events and Deaths**

#### **7.1.1. Adverse Event Dictionary**

Clinical and laboratory adverse events (AEs) will be coded using the MedDRA 21.0. System organ class (SOC), high-level group term (HLGT), high-level term (HLT), preferred term (PT), and lower-level term (LLT) will be provided in the AE dataset.

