##### **7.1.7.1. Adjudication Committee for MACE**

An independent cardiovascular safety endpoint adjudication committee (CVEAC) will be formed to periodically review and adjudicate all potential major cardiovascular adverse events (MACE). MACE is defined as cardiovascular death, nonfatal myocardial infarction and nonfatal stroke.

To identify the MACE, the following potential cases identified using MedDRA search listing (MST) searches will be adjudicated:

- All deaths
- Cardiovascular events (meeting serious criteria)
- Myocardial infarction
- Hospitalization for unstable angina
- Transient ischemic attack
- Stroke
- Hospitalization for cardiac failure
- Percutaneous coronary intervention

The CVEAC will review those potential MACE and related clinical data to determine whether a MACE has developed. The CVEAC's role and responsibilities and the data to be provided to the CVEAC are described in a mutually agreed upon CVEAC charter. The CVEAC charter defines the CVEAC membership, adjudication process, meeting logistics, and meeting frequency. The number and percentage of subjects with positively adjudicated MACE will be summarized by treatment group using the PT term.

A by-subject listing for all patients who have a potential MACE or a positively adjudicated MACE at any time will be provided.

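### SAP 7.1.7.1 breaks positively adjudicated MACE down by MedDRA preferred term only and plans no summary by adjudicated component

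*Protocol*

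**What the plan says.** Protocol 8.11 sets up the adjudication committee and states its purpose: "The adjudication of these events will be performed in a blinded fashion for the purposes of data analysis". It says nothing about how the results are to be tabulated.

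The tabulation rule is in SAP 7.1.7.1, in five steps:

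- **Definition.** "MACE is defined as cardiovascular death, nonfatal myocardial infarction and nonfatal stroke".
- **Events sent for review.** Eight categories: all deaths, serious cardiovascular events, myocardial infarction, hospitalized unstable angina, transient ischemic attack, stroke, hospitalized cardiac failure and percutaneous coronary intervention.
- **Committee output.** "The CVEAC will review those potential MACE and related clinical data to determine whether a MACE has developed". The process is left to a charter that is not among the documents.
- **Table.** "The number and percentage of subjects with positively adjudicated MACE will be summarized by treatment group using the PT term".
- **Listing.** "A by-subject listing for all patients who have a potential MACE or a positively adjudicated MACE at any time will be provided". Its columns are not specified.

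On the origin of the PT, SAP 7.1.1 says: "Clinical and laboratory adverse events (AEs) will be coded using the MedDRA 21.0". Neither document describes a separate coding of the committee's diagnosis.

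**The concern.** The SAP defines the endpoint by adjudicated component and then displays it on a different classification. The three components depend on judgments that a PT does not hold: whether a death was cardiovascular, and whether an infarction or stroke was fatal.

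What is at stake is the component breakdown by arm. A reader who wants to know whether an imbalance in MACE comes from deaths, infarctions or strokes would have to reconstruct that from PT rows. The reconstruction could be wrong for any event that the committee classed differently from the reported term, and for any fatal event.

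**Working it through.** No arithmetic applies. The plan states no MACE rate, event count, test or estimate that could be reproduced. The check sets the definition beside the planned outputs.

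**Step 1. Does any planned output give component counts by arm?**

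| Output | Classification used | Adjudicated component by arm? |
|---|---|---|
| MACE table (SAP 7.1.7.1) | PT | No |
| MACE by-subject listing (SAP 7.1.7.1) | Columns not stated | No; a listing gives no counts |
| Serious events leading to death (SAP 7.1.6.1) | System organ class and PT | No; adjudicated cause not stated |
| Listings of deaths and of fatal serious events (SAP 7.1.6.1) | By subject | No |
| Other events of special interest (SAP 7.1.7.2) | PT | No; MACE not included |

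None does.

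**Step 2. Can the components be recovered from PT rows?**

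- *Cardiovascular death.* This needs the adjudicated cause and the fatal outcome, and a PT gives neither. An infarction that proves fatal belongs under cardiovascular death in the SAP's definition, but it could sit in the same PT row as nonfatal infarctions.
- *Nonfatal infarction and nonfatal stroke.* These are visible in part, because events reported as such fall under PTs that name them. One component can still be split over several PTs, and fatal cases are not separated out.
- *Events upheld under a different diagnosis.* Of the eight review categories, infarction and stroke match a component by name. Deaths and serious cardiovascular events are broader than any component. The other four (unstable angina, transient ischemic attack, cardiac failure, coronary intervention) are not components at all. An event from those four can enter the MACE table only if the committee upholds it as a component. If the PT is that of the reported event, the event then appears under a term that is not a MACE component.

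**Step 3. Is the component available?** By the SAP's definition, an event is a MACE only if it is one of the three components. A positive decision therefore implies a component. Whether the component is recorded as a data field is not stated in the SAP and would depend on the charter.

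**Step 4. What is unaffected?** The subjects counted are those with a positive adjudication. The number and percentage with any MACE by arm do not depend on how the rows are labelled.

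**The case against.** The strongest reply is that this is a table-layout preference. Adjudication already determines every entry in the table, infarctions and strokes reported as such can be seen by PT, and PT display is the SAP's convention for its other events of special interest. Fatal serious events are tabulated and listed elsewhere. MACE is not tested, and no decision rule depends on it. If events are few, a reader can follow each case in the listing.

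Most of this is correct and limits the point. It does not remove it, because none of those outputs gives counts by adjudicated component and arm, and the fatal-event table does not state the adjudicated cause. The convention for other events of special interest is also a weak precedent: SAP 7.1.7.2 does not describe them as adjudicated, whereas MACE has a component definition of its own.

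Four stronger readings are tempting, and the documents do not support them:

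- *That the table cannot show infarctions or strokes, or that adjudication adds nothing.* It shows some of them, and adjudication decides who is counted.
- *That the PT is certainly the site's term.* SAP 7.1.1 makes this the natural reading, but SAP 7.1.7.1 does not say whether the PT belongs to the reported or the adjudicated event.
- *That Protocol 8.11 is wrong or contradicted.* It states a purpose, and the SAP's table is consistent with it. The sentence to change is in SAP 7.1.7.1.
- *That a percentage distortion can be given.* The documents give no MACE rate and no reclassification frequency. A range derived from assumed total MACE would not carry over to the smaller component counts.

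**Conclusion.** The concern holds as a minor point. SAP 7.1.7.1 specifies a PT breakdown of positively adjudicated MACE and no summary by the three components of its own definition, so component counts by arm cannot be read reliably from the planned table. The overall MACE count by arm is sound, and the efficacy analyses are untouched. No numerical size is claimed.

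Two parts rest on inference. That the PT codes the reported event is inferred from the adverse-event coding rule. That the committee records a component is inferred from the MACE definition. If the PT were instead assigned to the adjudicated diagnosis, events upheld under a different diagnosis would no longer be misplaced. The lack of an adjudicated cause of death and of a fatal/nonfatal split would remain.

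**What to change.** In SAP 7.1.7.1, replace the PT breakdown with n (%) of subjects by treatment group for:

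- any positively adjudicated MACE;
- cardiovascular death;
- nonfatal myocardial infarction;
- nonfatal stroke.

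Each should follow the committee's classification. In the by-subject listing, show the PT beside the adjudicated category, and state which event the PT codes.

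The cost is one SAP sentence and one table shell, plus a check that the charter has the committee record the component for each positive decision. If the charter does so, no new data are needed.

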8.12. Analysis Schedule

The primary and secondary analyses will be conducted after all subjects either complete their Week 24 visit or prematurely discontinue from the study. The final analysis will be performed when all subjects complete the study or prematurely discontinue from the study.

9. RESPONSIBILITIES

9.1. Investigator Responsibilities

9.1.1. Good Clinical Practice

The investigator will ensure that this study is conducted in accordance with the principles of the Declaration of Helsinki (as amended in Edinburgh, Tokyo, Venice, Hong Kong, and South Africa), International Conference on Harmonisation (ICH) guidelines, or with the laws and regulations of the country in which the research is conducted, whichever affords the greater protection to the study subject. These standards are consistent with the European Union Clinical Trials Directive 2001/20/EC and Good Clinical Practice Directive 2005/28/EC.

The investigator will ensure adherence to the basic principles of Good Clinical Practice, as outlined in 21 CFR 312, subpart D, “Responsibilities of Sponsors and Investigators,” 21 CFR, part 50, 1998, and 21 CFR, part 56, 1998.

The investigator and all applicable subinvestigators will comply with 21 CFR, Part 54, 1998, providing documentation of their financial interest or arrangements with Gilead, or proprietary interests in the investigational drug under study. This documentation must be provided prior to the investigator’s (and any subinvestigator’s) participation in the study. The investigator and subinvestigator agree to notify Gilead of any change in reportable interests during the study and for 1 year following completion of the study. Study completion is defined as the date when the last subject completes the protocol-defined activities.

9.1.2. Institutional Review Board (IRB)/Independent Ethics Committee (IEC) Review and Approval

The investigator (or sponsor as appropriate according to local regulations) will submit this protocol, informed consent form, and any accompanying material to be provided to the subject (such as advertisements, subject information sheets, or descriptions of the study used to obtain informed consent) to an. The investigator will not begin any study subject activities until approval from IRB/IEC has been documented and provided as a letter to the investigator.

Before implementation, the investigator will submit to and receive documented approval from the IRB/IEC any modifications made to the protocol or any accompanying material to be provided to the subject after initial IRB/IEC approval, with the exception of those necessary to reduce immediate risk to study subjects.

9.1.3. Informed Consent

The investigator is responsible for obtaining written informed consent from each individual participating in this study after adequate explanation of the aims, methods, objectives, and potential hazards of the study and before undertaking any study-related procedures. The investigator must use the most current IRB/IEC –approved consent form for documenting written

informed consent. Each informed consent (or assent as applicable) will be appropriately signed and dated by the subject and the person conducting the consent discussion, and also by an impartial witness if required by local requirements. The consent form will inform subjects about genomic testing and sample retention, and their right to receive clinically relevant genomic analysis results.

9.1.4. Confidentiality

The investigator must assure that subjects' anonymity will be strictly maintained and that their identities are protected from unauthorized parties. Only subject initials, date of birth, another unique identifier (as allowed by local law) and an identification code will be recorded on any form or biological sample submitted to the Sponsor, IRB/IEC, or laboratory. Laboratory specimens must be labeled in such a way as to protect subject identity while allowing the results to be recorded to the proper subject. Refer to specific laboratory instructions. NOTE: The investigator must keep a screening log showing codes, names, and addresses for all subjects screened and for all subjects enrolled in the trial. Subject data will be processed in accordance with all applicable regulations.

The investigator agrees that all information received from Gilead, including but not limited to the investigator brochure, this protocol, eCRF, the study drug, and any other study information, remain the sole and exclusive property of Gilead during the conduct of the study and thereafter. This information is not to be disclosed to any third party (except employees or agents directly involved in the conduct of the study or as required by law) without prior written consent from Gilead. The investigator further agrees to take all reasonable precautions to prevent the disclosure by any employee or agent of the study site to any third party or otherwise into the public domain.

9.1.5. Study Files and Retention of Records

The investigator must maintain adequate and accurate records to enable the conduct of the study to be fully documented and the study data to be subsequently verified. These documents should be classified into at least the following two categories: (1) investigator's study file, and (2) subject clinical source documents.

The investigator's study file will contain the protocol/amendments, CRF and query forms, IRB/IEC and governmental approval with correspondence, informed consent, drug records, staff curriculum vitae and authorization forms, and other appropriate documents and correspondence.

The required source data should include sequential notes containing at least the following information for each subject:

- Subject identification (name, date of birth, gender);
- Documentation that subject meets eligibility criteria, i.e., history, physical examination, and confirmation of diagnosis (to support inclusion and exclusion criteria);

- Documentation of the reason(s) a consented subject is not enrolled
- Participation in study (including study number);
- Study discussed and date of informed consent;
- Dates of all visits;
- Documentation that protocol specific procedures were performed;
- Results of efficacy parameters, as required by the protocol;
- Start and end date (including dose regimen) of IMP, including dates of dispensing and return;
- Record of all adverse events and other safety parameters (start and end date, and including causality and severity);
- Concomitant medication (including start and end date, dose if relevant; dose changes);
- Date of study completion and reason for early discontinuation, if it occurs.

All clinical study documents must be retained by the investigator until at least 2 years or according to local laws, whichever is longer, after the last approval of a marketing application in an ICH region (i.e., United States, Europe, or Japan) and until there are no pending or planned marketing applications in an ICH region; or, if no application is filed or if the application is not approved for such indication, until 2 years after the investigation is discontinued and regulatory authorities have been notified. Investigators may be required to retain documents longer if specified by regulatory requirements, by local regulations, or by an agreement with Gilead. The investigator must notify Gilead before destroying any clinical study records.

Should the investigator wish to assign the study records to another party or move them to another location, Gilead must be notified in advance.

If the investigator cannot provide for this archiving requirement at the study site for any or all of the documents, special arrangements must be made between the investigator and Gilead to store these records securely away from the site so that they can be returned sealed to the investigator in case of an inspection. When source documents are required for the continued care of the subject, appropriate copies should be made for storage away from the site.

9.1.6. Case Report Forms

For each subject consented, an eCRF will be completed by an authorized study staff member whose training for this function is documented according to study procedures. eCRF should be completed on the day of the subject visit to enable the sponsor to perform central monitoring of safety data. The Eligibility Criteria eCRF should be completed only after all data related to eligibility have been received. Subsequent to data entry, a study monitor will perform source

data verification within the EDC system. Original entries as well as any changes to data fields will be stored in the audit trail of the system. Prior to database lock (or any interim time points as described in the clinical data management plan), the investigator will use his/her log in credentials to confirm that the forms have been reviewed, and that the entries accurately reflect the information in the source documents. The eCRF captures the data required per the protocol schedule of events and procedures. System-generated or manual queries will be issued to the investigative site staff as data discrepancies are identified by the monitor or internal Gilead staff, who routinely review the data for completeness, correctness, and consistency. The site coordinator is responsible for responding to the queries in a timely manner, within the system, either by confirming the data as correct or updating the original entry, and providing the reason for the update (e.g., data entry error). At the conclusion of the trial, Gilead will provide the site with a read-only archive copy of the data entered by that site. This archive must be stored in accordance with the records retention requirements outlined in Section 9.1.5.

9.1.7. Investigational Medicinal Product Accountability and Return

Where possible, IMP should be destroyed at the site. At the start of the study, the study monitor will evaluate each study center's IMP disposal procedures and provide appropriate instruction for disposal or return of unused IMP supplies. If the site has an appropriate standard operating procedure (SOP) for drug destruction as determined by Gilead Sciences, the site may destroy used (empty or partially empty) and unused IMP supplies as long as performed in accordance with the site's SOP. This can occur only after the study monitor has performed drug accountability during an on-site monitoring visit.

A copy of the site's IMP Disposal SOP or written procedure (signed and dated by the PI or designee) will be obtained for Gilead site files. If the site does not have acceptable procedures in place, arrangements will be made between the site and Gilead Sciences (or Gilead Sciences' representative) for return of unused study drug supplies.

If IMP is destroyed on site, the investigator must maintain accurate records for all IMPs destroyed. Upon study completion, copies of the IMP accountability records must be filed at the site. Another copy will be returned to Gilead.

The study monitor will review IMP supplies and associated records at periodic intervals.

9.1.8. Inspections

The investigator will make available all source documents and other records for this trial to Gilead's appointed study monitors, to IRB/IEC, or to regulatory authority or health authority inspectors.

9.1.9. Protocol Compliance

The investigator is responsible for ensuring the study is conducted in accordance with the procedures and evaluations described in this protocol.

9.2. Sponsor Responsibilities

9.2.1. Protocol Modifications

Protocol modifications, except those intended to reduce immediate risk to study subjects, may be made only by Gilead. The investigator must submit all protocol modifications to the IRB/IEC in accordance with local requirements and receive documented IRB/IEC approval before modifications can be implemented.

9.2.2. Study Report and Publications

A clinical study report (CSR) will be prepared and provided to the regulatory agency. Gilead will ensure that the report meets the standards set out in the ICH Guideline for Structure and Content of Clinical Study Reports (ICH E3). Note that an abbreviated report may be prepared in certain cases.

Investigators in this study may communicate, orally present, or publish in scientific journals or other scholarly media only after the following conditions have been met:

the results of the study in their entirety have been publicly disclosed by or with the consent of Gilead in an abstract, manuscript, or presentation form or the study has been completed at all study sites for at least 2 years

The investigator will submit to Gilead any proposed publication or presentation along with the respective scientific journal or presentation forum at least 30 days before submission of the publication or presentation.

No such communication, presentation, or publication will include Gilead's confidential information (see Section 9.1.4).

The investigator will comply with Gilead's request to delete references to its confidential information (other than the study results) in any paper or presentation and agrees to withhold publication or presentation for an additional 60 days in order to obtain patent protection if deemed necessary.

